#### 1. INTRODUCTION

This is a sub-study addendum to the SANS-UUI Phase I study. The primary objective of Phase I was to assess the utilization of the system during the SNS trial and follow-up periods and to help inform the length of hours of daily stimulation to be used in Phase II of the study. Phase I demonstrated that a short daily stimulation (2 hours per day) with the Neuspera System delivers appropriate urinary urgency incontinence (UUI) symptom relief. Please refer to the SANS-UUI Protocol (NSM-004) for the full details of Phase I design and methods.

#### 1.1. Rationale

The sub-study rationale is to objectively determine if half-hour daily stimulation is effective in satisfactorily addressing UUI. The population to be studied includes subjects from the SANS-UUI Phase I Study who have continued to meet success criteria (50% improvement of UUI episodes) on their most recent 72-hour bladder diaries, and who are interested in the potential to maintain their benefit with a reduced daily stimulation requirement.

During the SANS-UUI study, 2 hours of daily stimulation provided a greater than 50% reduction in UUI episodes in over 90% of the responding subjects; this outcome was similar to outcomes seen with commercially available devices utilizing continuous stimulation 24-hours a day. The SANS-UUI study was not designed to determine if less than 2 hours of daily stimulation could also be successful. There is recent evidence from the Bluewind study 2-year outcomes (John P. F. A. Heesakkers, March 2025) that a tibial nerve stimulation regimen of 30 minutes twice weekly may be effective for subjects initially completing therapy for 1 hour twice a day. Therefore, it seems likely that a reduced stimulation time will be similarly effective for sacral neuromodulation. Subjects will be allowed to return to two-hours a day of stimulation if desired.

#### 2. STUDY DESIGN

#### 2.1. Study Purpose

The purpose of this study is to investigate the effectiveness and subject acceptance of half-hour daily stimulation to treat UUI.

#### 2.2. Objective

To determine if stimulating a half-hour per day is effective and acceptable by subjects.

#### 2.3. Study Design

Prospective, multi-center, single-arm study with subjects acting as their own control.

The sub-study will be implemented with minimal disruption to the SAN-UUI Phase I study. All Phase I subjects are currently past their 48-Month follow-up, and the clinic visit internal is every 6 months. Eligible subjects will complete this sub-study over a 6-week period, between scheduled clinic visits.

SANS-UUI Phase I Sub-Study Addendum, version 1.0 / 04 April 2025 Confidential - Neuspera Medical Inc.

Page 8 of 11

Protocol no: NSM-004; Version 21.0 Page 138 of 141 04 Apr 2025
Confidential Neuspera

Figure 1 shows the study design and subject flowchart. Subjects who are currently responders (50% or greater reduction in UUI from baseline) with 2 hours daily stimulation on their most recent study visit will complete a sub-study baseline 72-hour bladder dairy. They will then be asked to reduce to half-hour daily stimulation for a two-week period. At the end of two weeks, they will complete the 72-hour bladder diary and answer two self-assessment questions, indicating if their therapy was effective and if they are willing to continue with half-hour daily stimulation for another two weeks. This will be repeated for two more weeks (6 weeks total) at which time subjects will exit the sub-study. At the end of the substudy, subjects will decide which duration of daily stimulation is preferred to use going forward (half-hour or 2 hours).

[figure not shown]

FIGURE 1: SUB-STUDY DESIGN AND SUBJECT FLOWCHART

#### 2.4. Statistical Considerations

Analyses for the sub-study will consist of descriptive statistics since stand-alone definitive conclusions regarding safety or efficacy from this sub-study are not desired, and the purpose of sub-study is to inform on the feasibility of a shorter duration stimulation time. Formal statistical conclusion from this sub-study will not be made so there are no type I error concerns.

#### 2.5. Subjects

Only Phase I subjects will be eligible to participate in this study. Eligible participants should meet the following criteria:

- Provide informed consent for this sub-study, showing their willingness to complete the additional bladder diaries, study questions, and intention to follow the daily stimulation and substudy requirements.
- Are responders (50% or greater reduction in UUI from baseline) at the most recent Phase I clinic visit.
- Have demonstrated consistent use of 2 hours daily stimulation in the last 30 days before substudy baseline bladder diary.

SANS-UUI Phase I Sub-Study Addendum, version 1.0 / 04 April 2025 Confidential - Neuspera Medical Inc.

Page 9 of 11

- Are currently free from symptoms of urinary tract infection (UTI) or other conditions that could confound UUI symptoms before sub-study baseline bladder diary.
- Are not experiencing any technical issues with the Neuspera system that would impact receiving stimulation.

#### 2.6. Procedures

Subjects will complete the sub-study between the scheduled clinic visits in SANS-UUI Phase I, which are completed at 6-month intervals. All the sub-study visits and required assessments below can be completed as Unscheduled Telephone visits or Unscheduled Clinic visits.

#### 2.6.1. Sub-study 72-hour Bladder Diary

Eligible participants are to complete a sub-study baseline 72-hour bladder dairy. Additionally, the 72-hour Bladder Diary will be collected at the end of each two-week stimulation period.

If a 72-hour Bladder Diary was completed for a regular Phase I clinic visit within 14 days of beginning this sub-study and the subject meets the eligibility criteria, that bladder diary can be used as the baseline diary.

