#### 7.5.9.4 Bladder Diary

Subjects will complete 72-hour bladder diaries at the required timeframes. The bladder diary is expected to be completed electronically but paper may be used as a backup.

The 72-hour bladder diary will collect voiding frequency (voids), void volume (specified times), urgency, urinary urgency incontinence (UUI) episodes (leaks), activity during UUI (at baseline only), and pad use. Subjects will record events for a consecutive 72-hour period, starting from when they first begin recording events.

Subjects will be trained on proper methods for completing the diary, collecting, and measuring the urine volume, and distinguishing between urge and stress incontinence episodes.

Baseline Bladder Diary: A baseline 72-hour bladder diary will be completed after the subject has stopped OAB medication for period determined appropriate based on type of OAB medication (at least five half-lives) to confirm the UUI inclusion criterion. At the discretion of the investigator, subjects who failed to accurately complete their diary may be allowed to repeat the diary evaluation. Those who failed to qualify after a second diary attempt will be withdrawn from further study participation.

Follow-up Bladder Diaries: Subjects will complete a 72-hour bladder diary prior to each scheduled clinic visit. Voided volume will only be collected at baseline and at Month 6 and 12 clinic visits. The bladder diary will be completed for a consecutive 72-hour period starting 4-7 days prior to each required follow-up visit. If a subject fails to complete the diary before the scheduled visit date, they may start the 72-

Protocol no: NSM-004; Version 21.0 Page 93 of 141 04 Apr 2025
Confidential Neuspera

hour diary within 24-hours of the scheduled visit date. If a subject continues to miss the start of the 72hour diary completion prior to a scheduled visit date, they will be assessed for protocol non-compliance.

If a subject is symptomatic with a UTI prior to beginning or in the middle of a 72-hour bladder diary, it is recommended to the subject start the diary after the subject is asymptomatic after standard-of-care treatment.

Subjects may be requested to complete an additional diary following programming changes to assess the impact of the changes. Subjects completing additional diaries will not need to collect void volume.

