#### SYNOPSIS

Addendum to the SANS-UUI Study Protocol:
Phase I Sub-Study to Assess Benefit of Half-Hour Daily Stimulation
Clinical Study of Neuspera's Implantable Sacral Nerve Stimulation (SNS) System in
Patients with Symptoms of Urinary Urgency Incontinence
SANS-UUI
NSM-004
Neuspera's Implantable Sacral Nerve Stimulation (SNS) System
Miniature wireless midfield powered implanted neurostimulation device for
urinary urgency incontinence (UUI).
Neuspera's Implantable SNS System is indicated to treat subjects with UUI who
have failed or could not tolerate more conservative treatments.
Neuspera Medical Inc.
Neuspera Medical Inc.
[name]
[name], USA
[contact]
Phase I centers selected by the Sponsor based on interest and ability to complete
the sub-study in acceptable timeframe.
To determine if stimulating a half-hour per day is effective and acceptable by
subjects.
Prospective, multi-center, single-arm study with subjects acting as their own
control.
Subjects who are currently responders (50% or greater reduction in UUI from
baseline) with 2 hours daily stimulation on their most recent study visit will
complete a sub-study baseline 72-hour bladder dairy. They will then be asked to
reduce to a half-hour daily stimulation for a two-week period. At the end of two
weeks, they will complete the 72-hour bladder diary and answer two self-
assessment questions, indicating if their therapy was effective and if they are willing to continue with half-hour daily stimulation for another two weeks. This
will be repeated for two more weeks (6 weeks total) at which time subjects will
exit the sub-study. At the end of the sub-study, subjects will decide which
duration of daily stimulation is preferred to use going forward (half-hour or 2
hours).
After completing a baseline 72-hour bladder diary, there will be three sub-study
visits completed at two-week internals (14 days +/-4). Visits may be completed by telephone or in clinic.

SANS-UUI Phase I Sub-Study Addendum, version 1.0 / 04 April 2025 Confidential - Neuspera Medical Inc.

Endpoints  Safety endpoints	Assessment of subjects' satisfaction with half-hour daily simulation compared with 2 hours daily simulation.     Self-assessment of UUI symptoms     72-hour bladder diary  No additional safety endpoints in sub-study. Safety endpoint reported in SAN-
	UUI main study.
Clinical investigation popul	ation
Sample size	Up to 17 Phase I subjects currently in follow-up may participate.

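### The half-hour sub-study lets the diary that qualified a subject also serve as the 2-hour baseline, which builds in a small apparent worsening for subjects who reuse it

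*Protocol*

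**What the plan says.** All references are to the Phase I sub-study addendum (Protocol, Appendix A) unless stated.

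- **Entry (2.5 Subjects).** Participants must meet this criterion: "Are responders (50% or greater reduction in UUI from baseline) at the most recent Phase I clinic visit". Response is judged from the 72-hour diary kept for that visit (main Protocol 7.5.8.1 and 7.5.9.4).
- **Baseline (2.6.1).** The default is a new diary: "Eligible participants are to complete a sub-study baseline 72-hour bladder dairy". The exception covers a diary kept for a regular clinic visit within 14 days of starting. If the subject is eligible, "that bladder diary can be used as the baseline diary".
- **Comparison (2.3 Study Design).** "Prospective, multi-center, single-arm study with subjects acting as their own control". There is no concurrent 2-hour group.
- **Size (Synopsis).** "Up to 17 Phase I subjects currently in follow-up may participate".
- **Analysis (2.4).** "Analyses for the sub-study will consist of descriptive statistics since stand-alone definitive conclusions regarding safety or efficacy from this sub-study are not desired". The change to be calculated is not defined.
- **Other 2-hour diaries.** Main Protocol 7.5.9.4 says "Subjects will complete a 72-hour bladder diary prior to each scheduled clinic visit", and Appendix A 2.3 says "All Phase I subjects are currently past their 48-Month follow-up". Earlier 2-hour diaries therefore exist. The appendix neither assigns them a role nor rules them out.

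**The concern.** A clinic diary recent enough to be reused will in practice be the diary from the most recent clinic visit, so it is the one on which the subject qualified. A 72-hour count varies from one diary to the next. Requiring that it be at most half the pre-implant count keeps subjects whose count happened to be low and drops some whose count happened to be high. The next diary is not selected in this way, so its mean is expected to be higher even when the true leakage rate is the same.

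In this sub-study the next diary is the first one on half-hour stimulation. The artefact would be read as a loss of benefit from the shorter session, and it always runs against half-hour stimulation. Subjects with a fresh baseline do not carry it. A pooled summary would therefore mix two kinds of baseline, in proportions that depend on when each subject happened to start.

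**Working it through.** The addendum states no power, precision or effectiveness threshold, so there is no figure of the plan's own to reproduce. The check asks how large the artefact is when the change to half an hour has **no** effect.

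**Inputs from the Protocol (3.1.2.1 Efficacy).** Episodes per day averaged 4.1 (SD 2.0) before implant and 0.8 (SD 0.9) at the Final Trial Visit, a mean decrease of 3.3 (SD 1.7). As a check, 4.1 − 0.8 = 3.3, and the three SDs imply a correlation of (2.0² + 0.9² − 1.7²) / (2 × 2.0 × 0.9) = 0.53. The Month 6 responder rate was 88.5%, and Appendix A 1.1 speaks of over 90% of responding subjects. The maximum sample size is 17.

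**Assumed, not in the documents.** Diary-to-diary variability on 2-hour stimulation, and the level of control beyond Month 48.

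**Model 1 (simulation).** The pre-implant count per 72 hours is normal with mean 12.3 (= 3 × 4.1) and SD 6 (= 3 × 2.0), floored at 4. The true reduction is Beta with mean 0.8 and concentration 8. Diaries are Poisson with an extra-Poisson CV. A subject is selected if diary 1 is at most half the pre-implant count. Diary 2 has the same true rate. The SE is the SD of change divided by √17.

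| Extra-Poisson CV | Mean of diary 2 − diary 1, per 72 h | SD of change | SE at n = 17 | Shift / SE |
|---|---|---|---|---|
| 0.2 | +0.26 | 2.17 | 0.53 | 0.49 |
| 0.3 | +0.29 | 2.30 | 0.56 | 0.52 |
| 0.5 | +0.43 | 2.70 | 0.65 | 0.66 |

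A rerun of the same model gave +0.24 to +0.40, or 11% to 21% of the mean of the qualifying diary.

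**Model 2 (different distributions, calibrated to 0.8, SD 0.9).** Rates are gamma, and diary reliability (ICC) is set at a nominal 0.3 to 0.8. About 91% to 92% qualify. The shift is +0.064 to +0.138 per day, or × 3 = +0.19 to +0.41 per 72 hours. In standard errors:

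- ICC 0.67: 0.064 / (0.662 / √17) = 0.40
- ICC 0.3: 0.138 / (0.925 / √17) = 0.62

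Between 36% and 43% of subjects look worse and 31% to 35% look better.

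**If long-term control is weaker (assumed).** With about 82% qualifying, the shift is +0.12 to +0.33 per day. With about 72% qualifying, it is +0.18 to +0.53 per day. The documents do not say whether either case applies.

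**Partial reuse.** The group shift equals the shift among reusers times the fraction reusing. At CV 0.3 with half reusing, 0.29 × 0.5 ≈ 0.15 per 72 hours.

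**Fresh baseline.** If the baseline is a diary not used for selection, it and the later diary have the same expectation when nothing changes. The expected shift is zero.

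**Responder rate.** In Model 1 a repeat diary meets the 50% criterion with probability 0.939, 0.935 and 0.924 at the three CVs.

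- Reused baseline: 100% at the start, then about 92% to 94%, an apparent fall of 6 to 8 points.
- Fresh baseline: about 92% to 94% at the start and again later, with no expected fall.

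**The case against.** The case on the other side is largely sound and limits the point.

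- **Reuse is an exception.** A fresh diary is the default. The 14-day limit, with clinic visits 6 months apart, means that only some subjects could use the option, and the figures for all 17 are an upper case. This stands.
- **The effect is small.** It is about half a standard error even if everyone reuses, and it cannot create a false impression in favour of half-hour stimulation. This stands at the documented response rates.
- **Nothing formal depends on it.** The analysis is descriptive, and the satisfaction and symptom self-assessments do not use the baseline diary. This stands, but descriptive status removes concern about type I error, not about bias. Appendix A 1.1 gives the aim as determining objectively whether half an hour is effective.

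A reader might also infer four stronger things that the documents do not support.

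- **That each unchanged subject will appear to lose benefit.** The shift is in the group mean; nearly a third or more of subjects would look better by chance.
- **That the 5% to 8% who later miss the 50% criterion (about 1 of 17) do so because of reuse.** Entry selects on the clinic diary either way, so that chance is the same with a fresh baseline. Only the 100% starting rate is due to reuse.
- **That the earlier 2-hour diaries are discarded.** The appendix is silent on them and does not exclude them.
- **That the mean of earlier diaries should be the main control.** Averaging a fresh diary with three earlier ones lowers the SD of change from 2.30 to 1.95 at CV 0.3, but only if nothing drifted. Those visits reach back about 18 months. They may predate the Wearable (Protocol version 20, March 2024), and 2-hour use, infection and technical status are not checked for them. If the three older diaries differ from present status by 0.39 episodes per 72 hours on average, the bias introduced is 0.75 × 0.39 = 0.29, equal to the bias removed.

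**Conclusion.** The point holds in a limited form. Sections 2.5 and 2.6.1 together let one diary select the subject and serve as the baseline. For subjects who reuse it, a comparison with that baseline is biased against half-hour stimulation by about 0.2 to 0.4 episodes per 72 hours, roughly half a standard error at 17 subjects if all reuse and proportionately less if fewer do. Their baseline responder rate is fixed at 100%, and the summary would combine two kinds of baseline.

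The size rests on assumed diary variability, on control at the levels reported early in Phase I, and on the analysis being change from the sub-study baseline, which the own-control design implies but the addendum does not define. The direction needs only that diaries vary by chance. Someone might take this as a weakness in the pivotal evidence; it is not, because the sub-study enrols only Phase I subjects, is descriptive, and plays no part in the Phase II analysis.

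**What to change.** 1. Delete the sentence in Appendix A 2.6.1 that allows a clinic-visit diary to be the sub-study baseline. Every subject then completes a fresh 72-hour diary on 2-hour stimulation after qualifying.
2. State that response on the fresh diary is not an entry condition. Appendix A 1.1 refers to the most recent diaries, and screening on the fresh one would bring the same selection back.
3. In 2.4, define the diary summary as change from the fresh diary at Weeks 2, 4 and 6.
4. Optionally, show change from the mean of earlier scheduled 2-hour diaries, excluding the qualifying one, as a supplementary summary only, with a note that those diaries may reflect drift or different conditions.

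The cost is a short wording change and one extra 72-hour diary for subjects who would have reused one. The earlier diaries in item 4 come from scheduled visits and need no new collection.

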#### 2.6.2. Weekly Stimulation Diary

Subjects are to continue to complete the Weekly Stimulation Diary. The diary will be updated to provide the option of half-hour daily stimulation.

#### 2.6.3. Two-Week Stimulation Period

After the sub-study baseline, subjects are to reduce daily stimulation to a half-hour and use for two weeks. At the end of the two-week stimulation period a sub-study visit will occur at 14 days (+/- 4), and subjects are to complete the following items:

- A 72-Hour Bladder Diary. Voiding volume is not required. The 72-hour bladder dairy should start 7 to 4 days before the sub-study visit.
- 2. Two self-assessment questions:

b.

Do you feel your UUI symptoms are:		
	Much worse	
	A little worse	
	The same	
	A little better	
	Much better	
Are you satisfied with the result of half-hour daily stimulation or would you like to		
resume the previous regimen of 2 hours per day?		

Subjects who want to continue with half-hour daily stimulation will continue with another two-week stimulation period and repeat the 72-hour bladder diary and the self-assessment questions noted above at the next sub-study visit.

SANS-UUI Phase I Sub-Study Addendum, version 1.0 / 04 April 2025 Confidential - Neuspera Medical Inc.

Page 10 of 11

Protocol no: NSM-004; Version 21.0 Page 140 of 141 04 Apr 2025
Confidential Neuspera

Subjects who do not want to continue with half-hour daily stimulation will revert to 2 hours daily stimulation; they will continue to complete diaries every two weeks until sub-study completion. If using 2 hours daily stimulation, they do not need to complete the self-assessment questions.

A final two-week stimulation period will be completed, for a total of six weeks. At the end of the final period, subjects will repeat the 72-hour bladder diary and complete the self-assessment questions noted above. At this time, subjects will exit the sub-study and continue with their preferred duration of daily stimulation (half-hour daily stimulation or 2 hours of daily stimulation). For subjects who participate in this sub-study, it will not be considered a protocol deviation in the main study if they use half-hour daily stimulation during or after sub-study participation.

#### 2.6.1. Adverse Events and Changes to Medication

As required in the SANS-UUI main protocol, the following will also be completed and documented in the EDC at each unscheduled sub-study visit (Telephone or Clincal):

- Changes to medication (including OAB medications) and OAB therapies
- Adverse event assessment

#### 2.6.2. Data Collection

Subjects will complete the sub-study with the data collection methods established in the SANS-UUI study, using the ePRO bladder diary, weekly stimulation diary, and the EDC system.

The Unscheduled Follow-up visits in EDC will be used to capture the additional visits (Telephone and/or Clinic) required for the sub-study. The self-assessment questions will be added to the Unscheduled Follow-up visit eCRF.

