## 2.1.10 Patient Controller

The Patient Controller (Figure 10) runs Neuspera's software Application on off-the-shelf equipment. The Patient Controller comes with its own USB charging cord. The Patient Controller is used by the subject to turn their Wireless Transmitter on/off, adjust stimulation amplitude (within limits set by the physician) and select which of the physician's pre-programmed stimulation programs to use. The user can also monitor the Wireless Transmitter battery level, view his/her program use history and adjust the Wireless Transmitter for airplane and international travel.

[figure not shown]

FIGURE 10: PATIENT CONTROLLER RUNNING THE NEUSPERA APPLICATION

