#### 7.5.8.7 Programming Sessions

During follow-up visits, subjects will bring their Wireless Transmitter for interrogation and data transfer to the Clinician Programmer. Subjects may be asked to bring their Charging Pads to the follow-up visits for retraining purposes.

Data from the Wireless Transmitter will be periodically downloaded on subject therapy and usage. Device programs will be reviewed and adjusted per Investigator discretion.

Programming adjustments may occur as many times as needed during the study to optimize treatment. Programming will be performed in accordance with the Clinician Manual.

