#### 7.5.8.8 Unscheduled Follow-Up Visits in the Clinic or via Telephone

If a subject is seen for an unscheduled visit the following will be completed and documented in the EDC.

- Changes to medication (including OAB medications) and OAB therapies
- Adverse event assessment

If the reason for the unscheduled visit is due to troubleshooting loss of efficacy or painful stimulation, the subject may be asked to complete the following procedures in addition to the above listed procedures.

- 72-hour bladder diary within 7 days. Voided volume not needed on diary.
- Radiographic imaging of the implanted device
- Device Parameter/Download
- Adjustments of device stimulation parameters on Clinician Programmer

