#### Following 12 Month Visit (> 12 Months)

After the subject has completed their 12-month follow-up visit, they will be required to complete a weekly stimulation diary. The weekly diary will collect how many days the subject used their system in the past week and the average duration of therapy.

The overall goal at each stimulation/therapy session is that subjects feel a comfortable level of stimulation throughout the stimulation period. Subjects will be encouraged to contact the study coordinator if they are having difficulty with the therapy sessions and/or log their difficulty on their stimulation diary. Instructions on completion of the stimulation diary will be reviewed with subjects to ensure understanding of completion requirements.

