#### 7.5.9.12 Stimulation Characteristics/Programming Parameters

Data from the Wireless Transmitter and Clinician Programmer will be collected and saved during each visit.

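### The half-hour sub-study's only named record of stimulation time is a self-reported weekly diary, so hidden departures from half an hour could be counted as half-hour results

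*Protocol*

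**What the plan says.** Appendix A (Rationale, section 1.1) sets out to settle on objective grounds whether half an hour a day is enough. Its second section 2.6.2, Data Collection, says that data will be gathered "using the ePRO bladder diary, weekly stimulation diary, and the EDC system". No device download is listed.

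The weekly diary is defined in the main protocol, section 7.5.9.5, for the time after Month 12: "The weekly diary will collect how many days the subject used their system in the past week and the average duration of therapy". For the sub-study (Appendix A, Weekly Stimulation Diary), "The diary will be updated to provide the option of half-hour daily stimulation". Daily start and stop times are recorded only through Month 12, and Appendix A section 2.3 states that all Phase I subjects are past Month 48.

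On visits, Appendix A section 2.6 says: "All the sub-study visits and required assessments below can be completed as Unscheduled Telephone visits or Unscheduled Clinic visits". Each sub-study visit involves a 72-hour bladder diary, two self-assessment questions (one asks whether the subject wishes to go back to 2 hours), medication changes and adverse events.

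The main protocol does collect device usage. Section 7.5.8.7: "Data from the Wireless Transmitter will be periodically downloaded on subject therapy and usage". Section 7.5.9.12: "Data from the Wireless Transmitter and Clinician Programmer will be collected and saved during each visit". Section 2.1.10 adds that the user of the Patient Controller can "view his/her program use history".

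Appendix A section 2.4 plans descriptive statistics only. SAP version 17.0 was written against protocol version 20.0, before the sub-study was added, so it supplies no further rule.

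**The concern.** The question is about a duration of stimulation, so the minutes actually delivered are the key exposure variable. Here they rest on weekly recall, although the system holds usage data. If a subject stimulates longer than half an hour and this is not reported, is mis-recalled or is lost in an average, the bladder diary for that period carries the effect of the longer session but may be tabulated under the half-hour regimen. That error favours a finding that half an hour is effective. Missed or shortened sessions could push the other way. At stake is the reading of the sub-study's own objective.

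**Working it through.** The sub-study states no power, error rate or effect size, so there is no planned figure to reproduce. The check compares passages and then gives an illustration.

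**1. What the exposure record can show.** The weekly diary yields two numbers per week: days used and average duration. The efficacy outcome is a 72-hour bladder diary that starts 7 to 4 days before the visit (Appendix A, 2.6.3). Take a week with four days at 0.5 h and three at 2 h:

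(4 × 0.5 + 3 × 2) / 7 = 8 / 7 = 1.14 h per day.

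That average shows that the week was not purely half-hour. It does not show whether the three bladder-diary days were the 2-hour days or half-hour days. If the subject rounds to the half-hour option, even the departure is lost.

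**2. Whether objective usage reaches the sub-study.** Sections 7.5.8.7 and 7.5.9.12 show that usage data can be retrieved from the transmitter. Sub-study visits, however, are unscheduled and may be by telephone. For unscheduled visits, section 7.5.8.8 lists a device download only under the condition "If the reason for the unscheduled visit is due to troubleshooting loss of efficacy or painful stimulation", and then only as something the subject may be asked to do. Appendix A adds no download of its own.

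**3. How diaries are classified.** Section 2.4 of the addendum has no definition of adherence to half an hour and no rule linking a bladder diary to the duration used. Subjects who return to 2 hours stay in and keep completing bladder diaries to the end (2.6.3). No text says how those diaries are tabulated.

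**4. Illustrative size.** Inputs: n = 17 (the cap in the Appendix A synopsis); response on longer use 0.90 (lower edge of the over-90% figure in its Rationale, an assumption here); p, the true response on half an hour (assumed); m, the number of unrecognised over-users (assumed).

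Reported response = ((17 − m) × p + m × 0.90) / 17, so the bias is m × (0.90 − p) / 17.

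| p | m = 0 | m = 2 | m = 4 | m = 6 |
|---|---|---|---|---|
| 40% | 40.0% | 45.9% | 51.8% | 57.6% |
| 50% | 50.0% | 54.7% | 59.4% | 64.1% |
| 60% | 60.0% | 63.5% | 67.1% | 70.6% |
| 75% | 75.0% | 76.8% | 78.5% | 80.3% |

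The smallest bias shown is 2 × 0.15 / 17 = 1.8 points and the largest is 6 × 0.50 / 17 = 17.6 points. The documents give no response rate for less than half an hour, so no figure is offered for under-use.

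If each subject had a 5%, 10% or 20% chance of over-use (assumed), the chance of at least one over-user among 17, 1 − (1 − q)^17, would be 58%, 83% or 98%.

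For scale, the exact 95% interval for 12 responders of 17 (70.6%) is 44.0% to 89.7%, that is, 27 points below and 19 above the estimate. Imprecision is larger than most of the bias in the table.

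**The case against.** The best defence has four parts.

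- **Longer use is not invisible.** The weekly diary records duration and gains a half-hour option. A question at the two-weekly visits asks about returning to 2 hours, and those who return need not answer the self-assessment questions while on 2 hours, so they can be identified. This stands. It confines the problem to use that is unreported, mis-recalled or averaged out.
- **The main protocol already covers usage.** The 6-monthly clinic visits continue and include a review of usage history (section 7.5.8.5), and Data Collection invokes the methods already established in the main study. This stands in part: the data could be used afterwards, but nothing commits to retrieving them for the sub-study periods or to using them in its analysis.
- **Drift toward longer sessions is conjecture.** Subjects switch the transmitter off themselves, agree to the reduced regimen, and may return to 2 hours openly. Entrants do come from a settled 2-hour habit and no automatic half-hour stop is described, but that does not show that none exists. This stands as to frequency, which is unknown.
- **Little depends on it.** The sub-study is descriptive, disclaims formal conclusions, has no success threshold, and also asks about acceptability, for which reporting as assigned is reasonable. This stands.

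A reader might infer that diaries recorded on longer stimulation would be reported as half-hour results, or that the plan cannot detect longer use. The documents support neither. No passage says that such diaries are pooled, and section 2.4 is simply silent. Reported longer use and formal reversion are both on record.

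**Conclusion.** The concern holds as a limited one. The addendum relies on recalled weekly exposure, does not call for usage data that the system holds, and has no rule for classifying bladder diaries by actual duration. Hidden departures from half an hour could therefore be counted as half-hour results, and over-use would favour the shorter regimen. The 2 to 18 point range rests on assumed numbers of over-users, assumed true response and an assumed 90% response on longer use; it shows scale and predicts nothing. The Phase II endpoints and conclusions are untouched. This is a worthwhile low-cost improvement, because it bears on the one question that the sub-study asks.

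**What to change.** In Appendix A, Data Collection (the second section 2.6.2) and section 2.4:

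1. Name the transmitter usage data as the exposure record, retrieved at a sub-study clinic visit or at the next 6-monthly visit. Keep the weekly diary as a supplement.
2. Report logged minutes per day for each two-week period and for the 72-hour bladder-diary days.
3. Show the descriptive bladder-diary and self-assessment results as assigned and also by logged duration, with subjects who returned to 2 hours shown separately. Keep both displays: subjects may lengthen sessions because symptoms return, so the concordant periods alone would be a selected group.

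None of this alters treatment. The cost is one extra table and a download of a kind the main study already makes. The look-back of the usage log is not stated and should be confirmed first. It must cover six weeks if read at the last sub-study visit, and longer if retrieval waits for the next scheduled visit. If it is too short, at least one sub-study visit would have to be in clinic.
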